6.3.4 Reporting of serious adverse events

All SAEs have to be reported, whether or not considered causally related to the investigational product, or to the study procedure(s). All SAEs will be recorded in the pCRF.

If any SAE occurs in the course of the study, then the Principal Investigator or other study centre personnel will inform the appropriate AstraZeneca representatives immediately, or **no later than 24 hours** of when he or she becomes aware of it.

The designated AstraZeneca representative works with the Principal Investigator to ensure that all the necessary information is provided to the AstraZeneca Patient Safety data entry site **within 1 calendar day** of initial receipt for fatal and life-threatening events **and within 5 calendar days** of initial receipt for all other SAEs.

For fatal or life-threatening AEs where important or relevant information is missing, active follow-up is undertaken immediately. The Principal Investigator or other study centre personnel inform AstraZeneca representatives of any follow-up information on a previously reported SAE immediately, or **no later than 24 hours** of when he or she becomes aware of it.

The reference document for definition of expectedness/listedness is the AZD9291 IB.

6.3.5 Laboratory safety assessment

Blood and urine samples for determination of clinical chemistry, haematology, and urinalysis will be collected at the time points indicated in the study plan (see [Table 2](#) and [Table 3](#)).

The laboratory variables to be measured are provided in Table 5.

Table 5 Laboratory safety variables

Haematology ^a	Clinical Chemistry ^a	Virology ^c	Urinalysis ^b	Drugs of Abuse
Basophils	Alanine aminotransferase (ALT)	Hepatitis B surface antigen	Bilirubin	Amphetamines
Eosinophils	Albumin	Hepatitis C antibody	Blood	Barbiturates
Haematocrit (packed cell volume- PCV)	Alkaline phosphatase Lactate dehydrogenase	Human immunodeficiency virus (HIV) antibody	Glucose	Benzodiazepines
Haemoglobin	Aspartate aminotransferase (AST)		Ketones	Cocaine

Haematology ^a	Clinical Chemistry ^a	Virology ^c	Urinalysis ^b	Drugs of Abuse
Lymphocytes	Bicarbonate		Leukocytes	Marijuana/cannabis.
Mean cell haemoglobin (MCH)	Bilirubin (total)		Nitrites	Methodone
Mean cell haemoglobin concentration (MCHC)	Bilirubin (direct) (only if total is elevated)		pH	Methamphetamine
Mean cell volume (MCV)	Calcium Chloride		Protein	Ecstasy
Monocytes	Lipase		Specific gravity	Morphine/opiates
Neutrophils	Creatinine		Urobilinogen	Phencyclidine
Platelet count	Gamma glutamyl transpeptidase (GGT)			Tricyclic antidepressants
Red blood cell (RBC) count	Glucose (fasting)			
White blood cell (WBC) count	Potassium Phosphate (inorganic) Protein (total) Amylase Sodium Urea			

- a Volunteers will fast from overnight prior to clinical laboratory evaluations at screening. Postdose time points will be Days 7, 14, 28 and End of Study visit (not fasted).
b Urinalysis to be performed by standard dipstick analysis. Microscopy should only be performed if the urinalysis shows a positive result.
c Only at screening.

At screening a blood sample will be collected to screen for hepatitis B surface antigen, hepatitis C antibodies, and HIV. Creatinine clearance will be calculated at screening using the Cockcroft-Gault formula:

$$\text{Estimated CrCL (mL/min)} = \frac{(140 - \text{age [years]}) \times (\text{body weight [kg]})}{\text{Serum creatinine (mg/dL)} \times 72}$$

Urine will be tested at screening and on Day -1 for drugs of abuse. Urine will be collected at the study centre. Alcohol will be assessed by an alcohol breath test. Smoking will be assessed by performing a breath carbon monoxide test. If a volunteer tests positive for drugs

of abuse, a retest may be performed and the volunteer may be excluded from entering the study, as judged by the Principal Investigator.

Laboratory values outside the reference limit suspected to be of any clinical significance will be repeated. Volunteers in whom suspected clinical significance is confirmed will either not be included or if already enrolled will be followed until normalisation or for as long as the Principal Investigator considers necessary. Additional laboratory variables may be performed for safety reasons if judged appropriate by the Principal Investigator. Further details are provided in the Laboratory Manual.

The safety laboratory samples will be analysed using routine methods at

NB. In case a volunteer shows an AST or ALT ≥ 3 x ULN or total bilirubin ≥ 2 x ULN please refer to [Appendix D](#) ‘Actions required in cases of combined increase of aminotransferase and total bilirubin – Hy’s Law’, for further instructions.

For blood volume see Section [7.1](#).

6.3.6 Physical examination

Physical examinations will be performed at the time points indicated in [Table 2](#). A complete physical examination will be performed at screening, Days 28, 35, 42, and End of Study visit that includes an assessment of the following: general appearance, respiratory, cardiovascular, abdomen skin, head and neck (including ears, eyes, nose and throat), lymph nodes, thyroid, abdomen, musculoskeletal (including spine and extremities), and neurological systems. A brief physical examination (including general appearance, skin, abdomen, cardiovascular system, and lungs) to be performed at admission or predose.

6.3.7 Resting 12-lead electrocardiogram

Twelve-lead ECGs will be recorded at the time points indicated in the study plan ([Table 2](#) and [Table 3](#)).

Electrocardiograms will be recorded in the supine position after the volunteer has rested in this position for at least 10 minutes. A total of 3 12-lead ECG will be recorded at 10 minute intervals at predose and 24-hours postdose.

Only the overall evaluation (normal/abnormal) will be captured in the pCRF. Any abnormalities (including corrected QT interval [QTc] values) should be reviewed by an appropriately qualified person.

The original ECG printouts with variables must be signed and dated and stored in the volunteer’s source workbook as source data.

6.3.8 Vital signs

Vital signs assessment will be performed at the time indicated in [Table 2](#) and [Table 3](#).

6.3.8.1 Pulse rate and supine blood pressure

Supine blood pressure and pulse rate will be measured using standard equipment after 10 minutes rest on a bed. Additional blood pressure/pulse rate assessments may be taken for safety at the discretion of the Principal Investigator or delegate.

6.3.8.2 Height and weight

Height (cm) and weight (kg) will be evaluated at screening and BMI (kg/m^2) will be calculated. Only weight will be evaluated at Day -1 and on Day 84. The volunteers will be required to remove their shoes and wear light indoor clothing for these measurements. When requested or judged necessary for the program, body weight and/or BMI can be measured at additional time points.

6.3.9 Ophthalmology

A full ophthalmologic examination including a slit-lamp fundoscopy, best corrected visual acuity, and intraocular pressure measurement must be performed at screening for all volunteers.

The same ophthalmic expert will perform ophthalmic assessments on each occasion where possible.

An ophthalmological examination should be performed if the volunteer reports eye symptoms such as dry eyes, grittiness, or irritation during the study. In case of clinically relevant ophthalmological abnormalities, an additional full examination will be performed. Any corneal changes must be monitored frequently, with therapeutic intervention as appropriate until resolution. Any abnormalities elicited will be recorded as an AE.

6.4 Pharmacokinetics

6.4.1 Collection of samples

Venous blood samples (approximately 13 mL of whole blood) for the determination of concentrations of AZD9291 and metabolites in plasma, blood and plasma [^{14}C] radioactivity, and metabolite characterisation will be taken at the times presented in [Table 2](#) and [Table 3](#). The actual date and time of collection will also be recorded.

Samples will be collected, labelled, stored, and shipped as detailed in the Clinical Sample Processing Manual. Amber tubes should be used to protect against the possibility of light-induced degradation.

At each time point when a PK sample is required, a 13 mL sample of whole blood will be taken, to be divided as follows:

- | | |
|-------------------|---|
| 1 x 1 mL blood | for total [^{14}C] measurement () |
| 2 x 0.5 mL plasma | for total [^{14}C] measurement () |

2 x 0.75 mL plasma for AZD9291, AZ5104, and AZ7550 concentration measurement ()

2 x 1 mL plasma for circulating metabolite profiling characterisation (and then AZ)

Collection of Urine

Each volunteer will pass all urine into specially provided containers during the intervals given in the study plan (Table 3). The start and stop date and time of the interval will be recorded. Samples will be collected, labelled, stored, and shipped as detailed in the Clinical Sample Processing Manual.

Volunteers will void all urine before dosing, and a 10 mL predose urine sample will be retained for drugs, metabolism and pharmacokinetic (DMPK) and further metabolite characterisation studies. Following receipt of the radioactive dose, each volunteer's urine will be collected as voided into pre-weighed screw top plastic containers, using separate containers for each specified (24-hour) collection period.

Urine samples will be collected and pooled from each volunteer over the following time periods: predose, 0 to 4, 4 to 8, 8 to 12, 12 to 24, 24 to 48, 48 to 72, 72 to 96, 96 to 120, 120 to 144, 144 to 168 hours, then continuing for each 24 hour period during residency up to and including Day 21 after dosing, and then nominally 648 to 672 (Day 28), 816 to 840 (Day 35), 984 to 1008 (Day 42) and 1992 to 2016 (Day 84).

Samples collected must be kept refrigerated (approximately 4°C) during each collection period. The total urine volume will be calculated (weight x density [1 g/cm³]) for each urine collection and will be recorded along with the actual start and stop dates and times of the pooled collection.

From each sample collection period when a urine sample is taken, it will be divided as follows:

2 x 5 mL urine for total [¹⁴C] measurement ()

2 x 5 mL urine for AZD9291, AZ5104 and AZ7550 concentration measurement ()

2 x 10 mL urine for circulating metabolite profiling characterisation (and then AZ)

From the remainder of each sample, 25 mL is to be kept in case re-analysis is required for any part above. The above urine volume for AZD9291, AZ5104 and AZ7550 concentration measurement () may be modified to accommodate assay requirements; the final sample collection and handling requirements will be identified in the Laboratory Manual.

All urine sub-samples will be stored at a temperature defined in the Clinical Sample Processing Manual when not required for analysis.

Collection of Faeces

Each volunteer will pass all faeces into specially provided containers during the interval given in the study plan (see [Table 3](#)). The actual time and date each stool sample is produced will be recorded.

Following receipt of the radioactive dose, each volunteer's faeces will be collected into pre-weighed rigid polypropylene containers (with lids), contained in bags. Individual containers will be used for each stool sample. All tissue wipes will be collected and put into the relevant faecal bag (tissue wipes are to be kept separate from the actual faecal samples). The weight of each stool sample collected must be recorded. Samples collected will be stored at -80°C.

To facilitate stool collection, softeners (eg, lactulose) may be used as per standard study centre practice (see [Section 3.1](#)). These must be documented as concomitant medication.

At each time point when samples are collected, it will be processed as follows:

Samples will be shipped for homogenisation within 24 hours of collection.

Stool samples will be collected by the volunteer over the following time periods: 0 to 24, 24 to 48, 48 to 72, 72 to 96, 96 to 120, 120 to 144, 144 to 168, 168 to 216, 216 to 264, 264 to 312, 312 to 360, 360 to 408, 408 to 456, 456 to 504, 648 to 672 (Day 28), 816 to 840 (Day 35), 984 to 1008 (Day 42) and 1992 to 2016 hours (Day 84). Each pooled sample will be homogenised with an appropriate volume of water (typically ca 1:1, w/v) and the homogenate will be sub-sampled as follows:

- | | |
|------------------------|--|
| 2 x 50 g of homogenate | For metabolite profiling characterisation () and then AstraZeneca). |
| 2 x 20 g of homogenate | Required to produce 2 g of freeze-dried sample for total [¹⁴ C] measurement. |

One or more aliquots from the homogenate will be retained as backup sample(s); the final sample collection and handling requirements will be identified in the Clinical Sample Processing Manual.

Collection of Vomitus

Should a volunteer vomit within 12 hours of dosing all vomitus will be collected into pre-weighed rigid polypropylene containers (with lids), contained in bags, including all tissue wipes used. Instances of vomiting will be recorded as an AE, and date and time of vomiting will be recorded on the appropriate AE CRF, in addition to on the container label. Samples collected must be weighed and will be stored frozen at -80°C.

The analysis of radioactivity in vomitus will be performed by _____ by AMS (working assumption) methodology. Full details will be included in the CSR.

For blood volume see Section 7.1.

6.4.2 Determination of drug concentration

Samples for determination of AZD9291, AZ5104 and AZ7550 concentration in plasma will be analysed by _____, using an appropriate bioanalytical method. Samples for determination of AZD9291, AZ5104 and AZ7550 in urine will be analysed by _____ using an appropriate bioanalytical method. Full details of the analytical methods used will be described in a separate bioanalytical report. All samples still within the known stability of the analytes of interest at time of receipt by the bioanalytical laboratory will be analysed.

The analysis of radioactivity in whole blood, plasma, urine, faeces and vomitus will be performed by _____ by liquid scintillation counting (LSC) or accelerator mass spectrometry (AMS) methodology. The mass balance output will be provided as a separate report from _____ which will be appended to the CSR. Full details of the analytical methods used in the determination of mass balance will be detailed in the CSR.

As part of a further study performed by AstraZeneca Oncology iMed, Alderley Park, profiling and characterisation of the metabolites in plasma, urine, faecal components will be carried out using appropriate analytical techniques. These results will be reported separately from the CSR.

6.5 Pharmacogenetics

6.5.1 Collection of pharmacogenetic samples

The blood sample for genetic research will be obtained from the volunteers at Day -1 after the optional informed consent has been signed. Although genotype is a stable parameter, early sample collection is preferred to avoid introducing bias through excluding volunteers who may withdraw due to an AE, such volunteers would be important to include in any genetic analysis. If for any reason the sample is not drawn at admission, it may be taken at any visit until the last study visit. Only 1 sample should be collected per volunteer for genetics during the study. Samples will be collected, labelled, stored, and shipped as detailed in the Laboratory Manual.

For blood volume see Section 7.1.

7. BIOLOGICAL SAMPLING PROCEDURES

7.1 Volume of blood

The total volume of blood that will be drawn from each volunteer in this study is as follows:

Table 6 Volume of blood to be drawn from each volunteer

Assessment		Sample volume (mL)	No. of samples	Total volume (mL)
Safety	Clinical chemistry	5	7	35
	Haematology	2	7	14
Pharmacokinetics		13	26	338 ^a
Pharmacogenetics (optional)		10	1	10
Total				397

a If an in-dwelling catheter is used, an additional 0.5 mL of blood will be collected to flush the catheter prior to collecting each sample.

The number of samples collected, as well as the volume required for each analysis, may be changed during the study (ie, if additional samples are drawn for repeated safety assessments). However, the maximum volume to be drawn from each volunteer during the study will not exceed 550 mL. To put this in context, a single withdrawal of 470 mL occurs during a regular blood donation.

7.2 Handling, storage and destruction of biological samples

The samples will be used up or disposed of after analyses or retained for further use as described here.

Biological samples for future research can be retained on behalf of AstraZeneca for a maximum of 15 years following the last volunteer's last visit in the study. The results from future analysis will not be reported in the CSR but separately in a scientific report.

7.2.1 Pharmacokinetic samples

Pharmacokinetic samples received by _____ will be disposed of after each entity produces a final Bioanalytical Report or 6 months after issuance of a draft Bioanalytical Report (whichever is earlier), unless requested for future analysis.

Pharmacokinetic samples may be disposed of or destroyed and anonymised by pooling. Additional analyses may be conducted on the anonymised, pooled PK samples to further evaluate and validate the analytical method. Any results from such analyses may be reported separately from the CSR.

Selected PK samples may be used and/or pooled for metabolite characterisation and/or quantification. These samples will be retained by Drug Metabolism and Pharmacokinetics, on

behalf of AstraZeneca, for a maximum of 1 year following the finalisation of the CSR. The results from this additional work will not be reported in the CSR.

Incurred sample reproducibility analysis, will be performed alongside the bioanalysis of the test samples. The results from the evaluation will not be reported CSR but separately in a bioanalytical report.

7.2.2 Pharmacogenetic samples

The processes adopted for the coding and storage of samples for genetic analysis are important to maintain volunteer confidentiality. Samples will be stored for a maximum of 15 years, from the date of the last volunteer's last visit, after which they will be destroyed. Deoxyribonucleic acid (DNA) is a finite resource that may be used up during analyses. Samples will be stored and used until no further analyses are possible or the maximum storage time has been reached.

For all samples irrespective of the type of coding used the DNA will be extracted from the blood sample. The DNA sample will be assigned a unique number replacing the information on the sample tube. Thereafter, the DNA sample will be identifiable by the unique DNA number only. The DNA number is used to identify the sample and corresponding data at the AstraZeneca genetics laboratories, or at the designated contract laboratory. No personal details identifying the individual will be available to any person (AstraZeneca employee or contract laboratory personnel working with the DNA.)

The samples and data for genetic analysis in this study will be single coded. The link between the volunteer enrolment code and the DNA number will be maintained and stored in a secure environment, with restricted access within the Clinical Genotyping Group Laboratory Information Management System (LIMS) at AstraZeneca. The link will be used to identify the relevant DNA samples for analysis, facilitate correlation of genotypic results with clinical data, allow regulatory audit and to trace samples for destruction in the case of withdrawal of consent when the volunteer has requested disposal/destruction of collected samples not yet analysed.

7.3 Labelling and shipment of biohazard samples

The Principal Investigator will ensure that samples are labelled and shipped in accordance with the Laboratory Manual and the Biological Substance, Category B Regulations (materials containing or suspected to contain infectious substances that do not meet Category A criteria), see [Appendix C](#) 'IATA 6.2 Guidance Document'.

Any samples identified as Infectious Category A materials are not shipped and no further samples will be taken from the volunteer unless agreed with AstraZeneca and appropriate labelling, shipment, and containment provisions are approved.

7.4 Chain of custody of biological samples

A full chain of custody is maintained for all samples throughout their life cycle.

The Principal Investigator keeps full traceability of collected biological samples from the volunteers while in storage at the centre until shipment or disposal (where appropriate) and keeps documentation of receipt of arrival.

The sample receiver keeps full traceability of the samples while in storage and during use until used or disposed of or until further shipment and keeps documentation of receipt of arrival.

AstraZeneca keeps oversight of the entire life cycle through internal procedures, monitoring of study sites, and auditing of external laboratory providers.

Samples retained for further use are registered in the AstraZeneca biobank system during the entire life cycle.

7.5 Withdrawal of informed consent for donated biological samples

If a volunteer withdraws consent to the use of donated biological samples, the samples will be disposed of/destroyed, and the action documented. If samples are already analysed, AstraZeneca is not obliged to destroy the results of this research.

As collection of the biological samples is an integral part of the study, then the volunteer is withdrawn from further study participation.

The Principal Investigator:

- Ensures volunteers' withdrawal of informed consent to the use of donated samples is notified immediately to AstraZeneca.
- Ensures that biological samples from that volunteer, if stored at the study site, are immediately identified, disposed of /destroyed, and the action documented.
- Ensures the laboratory(ies) holding the samples is/are informed about the withdrawn consent immediately and that samples are disposed/destroyed, the action documented and the signed document returned to the study centre.
- Ensures that the volunteer and AstraZeneca are informed about the sample disposal.

AstraZeneca ensures the central laboratory(ies) holding the samples is/are informed about the withdrawn consent immediately and that samples are disposed of/destroyed and the action documented and returned to the study centre.

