2.3 Exploratory objectives

1. To provide samples for subsequent studies to allow the characterisation of the metabolism of [¹⁴C]-AZD9291 through the assessment of metabolic profiles of selected plasma and excreta samples.
2. To collect and store an optional pharmacogenetic blood sample from consenting healthy volunteers for future exploratory research into genes/genetic variation that

may influence response (ie, distribution, safety, tolerability and efficacy) to AZD9291.

These results will be reported separately from the CSR.

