c Blood sampling for genotyping is optional and will be collected if the volunteer provides additional informed consent on Day -1.

d Height/weight will be evaluated at the screening visit. Only weight will be evaluated on Day-1 and Day 84 (End of Study visit).

e A brief physical examination (including general appearance, skin, abdomen, cardiovascular system, and lungs) performed at admission or predose.

- f The volunteers will fast from overnight prior to clinical laboratory evaluations at screening. Postdose time points will be Days 7, 14, 28 and End of Study visit (not fasted).
- g Creatinine clearance will be estimated using the Cockcroft-Gault formula at screening.
- h Ophthalmic examination (best corrected visual acuity and slit-lamp fundoscopy and intraocular pressure measurement) will be conducted at screening (will be considered the baseline value; no need to repeat) and for cause (on occurrence of AE only).
- i A sample for urinalysis to be collected together with the other clinical laboratory evaluations. Microscopy will only be performed if abnormal urinalysis results are observed.
- j Alcohol will be assessed by an alcohol breath test. Smoking will be assessed by performing a breath carbon monoxide test. A positive test will constitute a value of greater than 10 ppm.
- k Supine blood pressure and pulse rate will be evaluated after the volunteer has rested in a supine position for at least 10 minutes. If possible, the same arm and equipment should be used for each evaluation (refer to [Table 3](#) for time points).
- l Refer to [Table 3](#) for ECG time points.
- m Volunteers will receive a single administration of the investigational product on Day 1.
- n Blood, plasma, urine and faeces samples will be collected (refer to [Table 3](#) for time points).
- o Discharge on Day 85.
- p Only SAEs will be collected from screening until the End of Study visit whereas AEs will be collected from Day -1 through to the End of Study Visit.

Table 3 **Schedule of assessments**

Time (Day/hours)	12-lead ECG	P & BP^a	Safety blood & urine^c	24-hour urine collection^b	Faecal collection^b	PK and Met-ID Blood/plasma	Food and Fluid Restrictions^c	Physical examination	Residency
Screening ^d	X	X	X					X	
Day -1 ^{d,e}							F ^f	X ⁱ	T
Predose	X ^g	X	X	T	T	X	D ^h	X ^j	
Dose (Day 1)							D		
0.5						X			
1	X	X				X	D ^h		
1.5						X			
2	X	X				X			
3						X			
4	X	X				X	F ^f , M		
6						X	F		
8	X	X				X			
10						X			
12	X	X				X			
18						X			

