5.8 Discontinuation of investigational product (Not applicable)

5.9 Withdrawal from study

Volunteers are at any time free to withdraw from the study (investigational product and assessments), without prejudice to further treatment (withdrawal of consent). These volunteers will always be asked about the reason(s) and the presence of any AEs. If possible, they will be seen and assessed by the Principal Investigator. Adverse events will be followed up (Sections [6.3.3](#) and [6.3.4](#)).

Withdrawn volunteers will not be replaced.

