8.4 Informed consent

The Principal Investigator at the centre will:

- Ensure each volunteer is given full and adequate oral and written information about the nature, purpose, possible risk and benefit of the study.
- Ensure each volunteer is notified that they are free to discontinue from the study at any time.
- Ensure that each volunteer is given the opportunity to ask questions and allowed time to consider the information provided.
- Ensure each volunteer provides signed and dated informed consent before conducting any procedure specifically for the study. A separate ICF will be provided for genotyping.
- Ensure the original, signed ICF(s) is/are stored in the Investigator's Study File.
- Ensure a copy of the signed ICF is given to the volunteer.
- Ensure that any incentives for volunteers who participate in the study as well as any provisions for volunteers harmed as a consequence of study participation are described in the ICF that is approved by an EC.

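### Section 7.5 withdraws from the study any volunteer who withdraws consent to donated samples and does not exempt the optional pharmacogenetic sample

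*Protocol*

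**What the plan says.** Section 7.5 opens with a trigger that does not distinguish sample types: "If a volunteer withdraws consent to the use of donated biological samples, the samples will be disposed of/destroyed, and the action documented". It then gives the consequence and its reason: "As collection of the biological samples is an integral part of the study, then the volunteer is withdrawn from further study participation". A site instruction follows: "Ensures that biological samples from that volunteer, if stored at the study site, are immediately identified, disposed of /destroyed, and the action documented".

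Elsewhere the protocol treats one of the donated samples differently:

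- Section 2.3 lists it as an exploratory objective: "To collect and store an optional pharmacogenetic blood sample from consenting healthy volunteers for future exploratory research into genes/genetic variation".
- Section 3.1, Table 2, footnote c: "Blood sampling for genotyping is optional and will be collected if the volunteer provides additional informed consent on Day -1".
- Section 8.4: "A separate ICF will be provided for genotyping".
- Section 7.2.2 explains that the link between enrolment code and DNA number is kept partly so that genetic samples can be traced for destruction if consent is withdrawn, "when the volunteer has requested disposal/destruction of collected samples not yet analysed". It does not say whether such a volunteer stays in the study.

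On withdrawal in general, Section 5.9 states: "Withdrawn volunteers will not be replaced".

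**The concern.** The reason given for the exit rule is that sample collection is integral to the study. That is true of the blood, plasma, urine and faeces. It is not true of the pharmacogenetic sample: a volunteer who never gives it takes part in full. As written, a volunteer who gives it and later changes his mind about it alone falls under the same exit rule as one who refuses further use of his excreta.

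The primary endpoint is the amount and percentage of the radioactive dose recovered in urine, faeces and in total after a single dose in 8 men. A volunteer who leaves after dosing cannot be re-dosed or replaced, and his excreta collection stops wherever it stands. Losing that for a consent that serves no primary or secondary objective would be an avoidable cost. It also attaches a penalty to withdrawing a consent that the protocol calls optional.

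**Working it through.** The protocol gives no figure to reproduce here: N = 8 rests on precedent (Section 12.3) and no hypothesis is tested (Section 12.2.1). The check is mainly textual, with some arithmetic for scale.

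**Step 1. Does 7.5 reach the pharmacogenetic sample?** Section 7 covers both PK samples (7.2.1) and pharmacogenetic samples (7.2.2), and 7.5 is its only procedure for withdrawal of sample consent. The trigger in 7.5 names no sample type, and no other section shown supplies an exemption. On the literal text, yes.

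**Step 2. Does the stated reason fit?** No. Sections 2.3, 3.1 (Table 2, footnote c), 7.1 (Table 6) and 8.4 show the sample to be optional or separately consented.

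**Step 3. What would be lost and what kept?**

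| Item | Effect of exit | Source |
|---|---|---|
| Further excreta, PK and scheduled safety collection | Stops | 7.5 |
| Data up to discontinuation | Kept in the analyses | 12.2.1 |
| Results of samples already analysed | Need not be destroyed | 7.5 |
| Adverse events | Asked about and followed up | 5.9 |
| Poststudy physical evaluations | Done at the point of discontinuation | 3.1, Table 2, footnote b |
| Replacement volunteer | None | 5.9 |

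**Step 4. Scale of the uncollected dose.** Assumptions: the whole dose is excreted mono-exponentially, plasma half-life stands in for the excretion half-life, and exit is at 168 h (Day 7, chosen for illustration). Half-lives are from Section 3.2: 50 h (AZD9291 median), 73.21 h (AZ7550 mean from longer sampling) and 120 h (the preliminary AZ7550 median, the longest half-life quoted).

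Fraction not yet excreted at time t = 2^(−t / half-life).

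| Half-life | Left at 168 h | Left at 504 h (end of continuous collection) | Difference |
|---|---|---|---|
| 50 h | 2^(−3.36) = 9.7% | 2^(−10.08) = 0.1% | 9.6 points |
| 73.21 h | 2^(−2.295) = 20.4% | 2^(−6.884) = 0.8% | 19.5 points |
| 120 h | 2^(−1.4) = 37.9% | 2^(−4.2) = 5.4% | 32.5 points |

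Differences are taken before rounding. The last column is what the exit itself costs in continuous collection, since a completer would also miss most of what is excreted after 504 h.

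The 120 h row is the top of the range. It applies a metabolite's half-life to the whole dose, and Section 1.2 puts AZ7550 AUC(0-72) at 51 against 2177 nM*h for the parent: 51/2177 = 2.3%.

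**Step 5. Effect on the summary of 8.** If the truncated recovery enters the mean, the mean falls by the uncollected share divided by 8: 9.7/8 = 1.2, 20.4/8 = 2.5 or 37.9/8 = 4.7 percentage points. If the volunteer is instead left out, the 95% t-interval half-width for a mean, t(0.975, n−1)/√n in SD units, goes from 0.836 (n = 8) to 0.925 (n = 7), and 0.925/0.836 = 1.106, about 11% wider.

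**The case against.** The strongest reply is that the rule contains its own limit. Exit is ordered because sampling is integral, and the genotyping sample plainly is not, so a sensible reader would apply 7.5 only to the mandatory samples. That reading is available, and it makes this a matter of wording that goes too far rather than a settled intention. But 7.5 does not state the limit, and site staff have to act on it at once.

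A second reply is that the separate genotyping consent form may say what withdrawing that consent means. It is not available here, so the criticism is confined to the wording of 7.5. A protocol sentence that says something broader should still be corrected.

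A third is that the event is remote. A volunteer must give the optional consent, then withdraw only that consent while still in the study, and the site must apply the strict reading. The documents give no rate. This stands and limits the weight of the point.

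Three stronger readings are tempting, and the documents do not support them:

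- A reader might infer that the volunteer's mass-balance and safety data are lost altogether, 12.5% of the study. Step 3 shows otherwise: only later collection stops. Calling it a loss of 77 of 84 days would mislead too, because after Day 21 only four 24-hour visits remain.
- A reader might infer that 7.2.2 contradicts 7.5 by letting the volunteer stay. It is silent on participation.
- A reader might infer that all blood, urine and faeces at the site must be destroyed. The opening sentence of 7.5 concerns the samples whose consent is withdrawn, and the bullets more naturally carry that out. Faeces are also shipped within 24 hours of collection (Section 6.4.1). What stands is that the site bullet does not expressly say so.

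**Conclusion.** The point holds as a defect in a stated rule. Section 7.5 as written sends out of the study a volunteer who withdraws only an optional, separately consented, exploratory sample, for a reason that does not apply to that sample, and nothing else in the protocol exempts him. The consequence would be an early stop to primary-endpoint collection in one of 8 unreplaceable volunteers, with everything gathered up to then retained.

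The size depends on when he leaves. At 168 h it is about 10% to 20% of his dose on the 50 h and 73.21 h half-lives and 38% at most among the half-lives quoted. These figures rest on mono-exponential, complete excretion and on plasma half-lives standing in for excretion of total radioactivity; they show scale and do not predict a result. The planned analysis is unaffected unless the event occurs, which is probably uncommon. Because the correction is so cheap, the text should be changed.

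**What to change.** Three edits to Section 7.5, with matching wording in both consent forms:

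1. Limit the exit sentence to withdrawal of consent for the blood, plasma, urine or faecal samples needed for the primary and secondary objectives.
2. Add, for example: *If a volunteer withdraws only the optional pharmacogenetic consent, only the pharmacogenetic/DNA sample is destroyed (Section 7.2.2). The volunteer continues in the study, and all other samples are kept and analysed.*
3. Limit the destruction bullets, at the site and at the laboratories, to samples covered by the withdrawn consent.

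The cost is about two sentences, a qualifier in the bullets and the matching consent text. There are no added procedures, samples or volunteers.
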